## 273 **7. Analysis of the Secondary Endpoints**

### 274 **7.1 Secondary CGM Outcomes**

275 For each secondary CGM outcome, mean  $\pm$  SD or summary statistics appropriate to the  
276 distribution will be reported by treatment arm. All secondary CGM metrics calculated over the  
277 full 24 hours of the day, daytime, and nighttime will be compared between treatment arms using  
278 the same repeated measures least squares regression model described above for the co-primary  
279 outcomes.

280 Replication of the primary outcome omitting the first four weeks of each period (as described in  
281 section 4.1.1) will be considered a secondary analysis. In this analysis, the baseline value  
282 included in the model will be the same baseline value as in the primary analysis.

283 The CGM outcomes listed in Section 4 under "Additional Exploratory Endpoints" will be  
284 tabulated separately by treatment arm with no formal statistical comparison.

### 285 **7.2 Secondary Insulin Outcomes**

286 For each secondary insulin outcome, mean  $\pm$  SD or summary statistics appropriate to the  
287 distribution will be reported by treatment arm. All secondary insulin metrics calculated over the  
288 full 24 hours of the day, daytime, and nighttime will be compared between treatment arms using  
289 the same repeated measures least squares regression model described above for the co-primary  
290 outcomes.

291 The insulin outcomes listed in Section 4 under “Additional Exploratory Endpoints” will be  
292 tabulated separately by treatment arm with no formal statistical comparison. For these outcomes,  
293 change will be calculated from the start of the period.

### 294 **7.3 Secondary HbA1c Outcomes**

295 For HbA1c, a longitudinal model adjusting for period and pre-study 670G system use as fixed  
296 effects will be used to compare treatments. The model will include three time points: (1)  
297 baseline, (2) period 1 follow-up, (3) period 2 follow-up.

298 The binary HbA1c outcomes listed in Section 4 under “Additional Exploratory Endpoints” will  
299 be tabulated separately by treatment arm with no formal statistical comparison. For these  
300 outcomes, improvement in HbA1c will be assessed from the start of the period.

### 301 **7.4 Secondary Clinical Outcomes**

302 For BMI, the same model described in section 7.3 for HbA1c will be used for a treatment arm  
303 comparison. The model will additionally adjust for HbA1c at randomization, age, and gender as  
304 fixed effects.

### 305 **7.5 Boxplots of Monthly Trends**

306 For each of the following secondary outcomes computed over the full 24 hours of the day,  
307 monthly trends will be evaluated using boxplots:

- 308 • Percentage of time spent with sensor glucose levels between 70 and 180 mg/dL
- 309 • Mean of sensor glucose levels
- 310 • Total Daily Insulin

311 For each of these secondary outcomes, we expect to have 12 weeks’ worth of data for each  
312 subject for each treatment arm. This amounts to approximately three months’ worth of data. Each  
313 period will be partitioned into three disjoint months using the same approach described in section  
314 6.2.3. A single value for each of these three months will be calculated for each of these three  
315 secondary outcomes for each treatment arm by pooling the CGM readings corresponding to each  
316 month. These calculated values will be used to generate boxplots displayed by treatment arm and  
317 period for each of the three months over time.

### 318 **7.6 Analysis Windows**

319 Only HbA1c and BMI measurements obtained within the following analysis windows at each  
320 time point included in the analyses:

- 321 • 12 weeks:  $\pm$ 14 days from the 84th day of the period

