927 3.0 HCL or 670G 4.0 AHCL pump as determined by the randomization order. The predictive  
928 low glucose suspend feature will be turned on. Participants starting with the 670G 4.0 AHCL  
929 pump will return the 670G 3.0 HCL pump used during Run-In.

931 The system will initially be used with auto mode deactivated (except for 670G auto mode users  
932 at screening who may activate auto mode if using the 670G 3.0 HCL pump) until participants are  
933 contacted 6-10 days into Study Period 1 with instructions to ensure auto mode is initialized.

934 Participants will also be instructed to ensure a new sensor is inserted 24 hours prior to initializing  
935 auto mode. Participants will then continue using the AID system for 12 weeks after auto mode is  
936 initialized. Participants will be expected to use auto mode at all times at home with some  
937 exceptions (e.g. times of illness, acetaminophen use).  
938

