### 953 **5.1.4 Visit and Phone Contact Schedule during Study Periods 1 and 2**

954 During each of the two study periods, visits and contacts will be scheduled as outlined below.  
955 Additional contacts or visits may occur as needed:

- 956 • Study Period begins
  - 957 ○ 6-10 days – participants will be contacted by phone to ensure auto mode is  
958 initialized
  - 959 • Auto mode is initialized (remaining visits and contacts are relative to the day auto mode  
960 is confirmed to be initialized by site staff)
    - 961 ○ 24-hour contact (*Contact must be completed by phone*)
    - 962 ○ 5-day contact ( $\pm 2$  days) = 3-7 days (*Contact must be completed by phone*)
    - 963 ○ 2-week visit ( $\pm 4$  days) = 10-18 days
    - 964 ○ 4-week contact ( $\pm 4$  days) = 24-32 days
    - 965 ○ 6-week visit ( $\pm 4$  days) = 38-46 days
    - 966 ○ 9-week contact ( $\pm 4$  days) = 59-67 days
    - 967 ○ 12-week visit/contact (+7 days) = 84-91 days (end of study period)

968 The goal will be for all participants to complete all scheduled visits. However, participants who  
969 (because of unforeseen circumstances) are unable or unwilling to return for all follow-up visits  
970 will be permitted to return for key visits only as an alternative to withdrawal from the study.  
971 When a participant is placed into this status, missed visits will not be recorded as protocol  
972 deviations (since they would not be recorded as protocol deviations if the participant was  
973 dropped from the study).  
975

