### 1579 10.3 Sample Size

1580 The sample size calculation is detailed in a separate document and summarized below.

1581 For computing sample size, estimates of the standard deviation (SD) for time spent in  
1582 hypoglycemia and hyperglycemia were made based on data from previous studies, Medtronic  
1583 670G Pivotal Trial, DIAMOND, JDRF CGM RCT, and REPLACE-BG.

1584

1585 Analyses of both primary outcomes must have a significant result ( $p < 0.05$ ) to declare benefit of  
1586 the intervention. The two co-primary outcomes therefore do not inflate the type 1 error, but  
1587 requiring both to be significant can inflate the type 2 error. A Bonferroni correction was  
1588 therefore applied to the power calculations by adding the type 2 error rate (i.e., 100% minus  
1589 power) for the two analyses. This represents a conservative estimate for composite power as the  
1590 probability that both tests will reject the null hypothesis.

1591

1592 The total sample size was computed to be 65 for the following assumptions (1) 90% power, with  
1593 adjustment to account for the two co-primary analyses, (2) a 5% absolute reduction in time  $>180$   
1594 mg/dL (10.0 mmol/L) with a standard deviation of paired differences of 12%, and a 2-sided type  
1595 1 error rate of 5%, and (3) a non-inferiority limit of 2% for the treatment group comparison of  
1596 time  $<54$  mg/dL (3.0 mmol/L) with an SD of paired differences of 1.3% and 1-sided type 1 error  
1597 of 2.5%.

1598  
1599 A sample size of 100 completing the trial has been selected to provide increased precision for  
1600 safety analyses and subgroup analyses. With a sample size of 100 participants completing the  
1601 crossover trial, the primary analysis will have 98% power.

1602  
1603 **10.4 Outcome Measures**

1604 All CGM derived indices will be calculated over the first 84 days of each period. The beginning  
1605 of the period is defined as the time that auto mode is first turned on, which per protocol is 6-10  
1606 days after the period starts. A post-meal period is defined as follows: meal starts at the time the  
1607 carbohydrate is entered and post-meal period ends at three hours after a meal unless another  
1608 carbohydrate is entered  $<3$  hours, which is then considered the end of the post-meal period.

1609  
1610 Hypoglycemia metrics are considered both safety and efficacy outcomes.

1611  

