91 12) Total Basal Insulin Units per Kilogram of Weight

92 13) Total Bolus Insulin Units per Kilogram of Weight

93 HbA1c Metrics

94 14) HbA1c

95 Clinical Metrics

96 15) BMI

97 Additional Exploratory Endpoints:

98 CGM Metrics:

99 *Continuous Outcomes:*

100 1) Time below 50 and 60 mg/dL

101 2) Time above 300 mg/dL

102 3) Area under the curve of sensor glucose levels above 180 mg/dL

103 4) Area over the curve of sensor glucose levels below 70 mg/dL

104 5) Standard deviation of sensor glucose levels

105 *Binary Outcome:*

106 1) Time in range (70-180 mg/dL) >70% and time below 54 mg/dL <1%.

107 HbA1c Metrics:

108 *Binary Outcomes:*

109 1) Improvement in HbA1c  $\geq 0.5\%$

110 2) Improvement in HbA1c  $\geq 1.0\%$

111 3) Relative reduction in HbA1c  $\geq 10\%$

112 4) HbA1c  $< 7.0\%$

113 All secondary efficacy and exploratory CGM metrics will be calculated over each treatment  
114 period for the full 24 hours, daytime (6:00 AM – 11:59 PM), and nighttime (12:00 AM – 5:59  
115 AM). They also will be calculated for each post-meal period measured for up to three hours after  
116 the start of a meal. The same will be done for all secondary efficacy insulin endpoints. It is

117 important to note that all hypoglycemic outcomes are considered both efficacy and safety  
118 outcomes.

119 **4.1 Calculation of the Co-Primary Outcomes**

120 As noted above, the co-primary outcomes are:

121 • Daytime Hyperglycemia (percent CGM readings above 180 mg/dL)  
122 • Hypoglycemia (percent CGM readings below 54 mg/dL; daytime/nighttime combined)

123 For each co-primary outcome, a single value will be calculated for each subject for each period  
124 by pooling all CGM readings in the first 84 days of each period or up to and including the 12-  
125 week visit date (whichever comes first).

126 In these calculations, each period will start at the time that the subject turns on auto mode. If the  
127 exact time is not known, then the period will start at midnight the day after the subject initiates it.  
128 We expect auto mode to be initiated 6-10 days after the randomization visit in period 1 and 6-10  
129 days after the first day of period 2. Participants who are 670G auto mode users at screening may  
130 initiate auto mode at the beginning of a study period in which the 670 3.0 HCL pump is being  
131 used. The end of the period will be defined as either 11:59 PM on the 12-week visit date or  

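### The HbA1c and BMI window in SAP 7.6 runs from auto-mode activation but visits run from site confirmation, so a few on-schedule samples from 670G 3.0 periods of early activators could be rejected

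*SAP*

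**What the plan says.** **Analysis clock.** SAP 7.6 admits "Only HbA1c and BMI measurements obtained within the following analysis windows at each" time point. It lists one window, at 12 weeks: ±14 "days from the 84 th day of the period". It does not restate when a period starts. SAP 4.1 gives the SAP's operational definition: "In these calculations, each period will start at the time that the subject turns on auto mode". Protocol 10.4 does the same for the CGM indices, where the beginning "of the period is defined as the time that auto mode is first turned on, which per protocol is 6-10" days into the study period.

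**Visit clock.** Protocol 5.1.4 says that on days 6 to 10 "participants will be contacted by phone to ensure auto mode is" initialized. The next entry sets the anchor for everything later: "Auto mode is initialized (remaining visits and contacts are relative to the day auto mode" is confirmed by site staff to be on. The 12-week visit is due 84 to 91 days after that anchor. Footnote 1 of Protocol Table 2 words the anchor differently: it counts visits from the day auto mode is initialized and does not mention confirmation.

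**The exception.** Protocol 5.1.2 keeps auto mode off until the call, except for 670G auto-mode users "at screening who may activate auto mode if using the 670G 3.0 HCL pump) until participants are" contacted. Protocol 5.1.3 repeats this for Period 2. SAP 4.1 carries it over: these participants may "initiate auto mode at the beginning of a study period in which the 670 3.0 HCL pump is being" used.

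**The concern.** An analysis window should screen out samples taken off schedule. Here it is tied to one date and the visit to another, and for one group the two dates can differ by up to 10 days. A participant who activates on day 0 and attends within the permitted visit window can still have the end-of-period HbA1c and BMI set aside, although nothing is wrong with either measurement.

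The loss would not be spread evenly. Early activation is allowed only on the 670G 3.0 pump, so rejected values would come only from the control system. They would also come only from prior 670G auto-mode users, a group that SAP 6.2 names as a randomization stratum and model covariate. SAP 4.2 rules out imputation for secondary analyses, so each rejected value removes one within-person comparison. The co-primary CGM outcomes are not affected, because this window applies only to HbA1c and BMI.

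**Working it through.** **Inputs**
- Accepted days after the SAP period start: 84 − 14 = 70 to 84 + 14 = 98 (SAP 7.6, with the start from SAP 4.1).
- Confirmation day *c*, counted from the start of the study period: 6, 7, 8, 9 or 10 (Protocol 5.1.4).
- Visit day *v*, counted from confirmation: 84 to 91 (Protocol 5.1.4).
- Activation day *a*: 0 for a prior 670G auto-mode user who activates at once on the 3.0 pump; otherwise *a* is about equal to *c*.
- Cap on 670G users entering the trial: 25% of about 112 = 28 (Protocol 2.1).

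**The plan's own figure.** 12 × 7 = 84 and 84 + 7 = 91, which matches the visit window in Protocol 5.1.4.

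**Days from activation to visit** = *c* − *a* + *v*.

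Everyone else (*a* = *c*): the visit falls on days 84 to 91, and 0 of 40 combinations are rejected. A gap of up to 7 days between activation and confirmation is still safe, since 91 + 7 = 98.

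Early activator (*a* = 0): the visit falls between 6 + 84 = 90 and 10 + 91 = 101.

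| Confirmation day | Visit, days after activation | Rejected (day > 98) |
|---|---|---|
| 6 | 90–97 | 0 of 8 |
| 7 | 91–98 | 0 of 8 |
| 8 | 92–99 | 1 of 8 |
| 9 | 93–100 | 2 of 8 |
| 10 | 94–101 | 3 of 8 |
| All | 90–101 | 6 of 40 (15%) |

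**Sensitivity to day counting**
- If the activation day is day 1, the 84th day is 83 days after activation and the limit is 97: 10 of 40 (25%).
- If the exact time is unknown, SAP 4.1 starts the period at the next midnight. The centre moves to 85 days after activation and the limit to 99: 3 of 40 (7.5%).

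**Sensitivity to activation day** (main count): activation on day 1 gives 3 of 40, on day 2 gives 1 of 40, and on days 3 to 5 gives 0 of 40.

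**Size.** Each prior user has one 670G 3.0 period. If all 28 activate on day 0 and the 40 combinations are equally likely, the expected loss is 28 × 6/40 = 4.2 values of each measure. The day-counting range is 28 × 3/40 = 2.1 to 28 × 10/40 = 7.0. With no early activation, or with calls on days 6 and 7 only, the main count gives 0.

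**After the fix.** Counted from the confirmed date, every on-schedule sample falls on days 84 to 91, so 0 of 40 are rejected in either arm.

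**The case against.** The strongest objection concerns the anchor. The Table 2 footnote counts visits from the day auto mode is initialized, and Protocol 5.1.2 and 5.1.3 speak of 12 weeks after initialization. If an early activator's visits were counted from true activation, they would fall on days 84 to 91 and nothing would be lost. Staff might also confirm auto mode at the visit that opens the period, since these participants may already have used it in the run-in (Protocol 3.2 and 3.3). This is a fair alternative, and it is why the lower end of the range is zero. It is not the better reading: the same footnote puts initiation 6 to 10 days into each period, the call in 5.1.4 applies to everyone, and 5.1.4 is the more explicit text. A reader should therefore not infer that compliant samples are lost on every reading.

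A reader might also infer a larger problem by taking the period in SAP 7.6 to begin at pump start, which would extend the rejections to everyone in both arms. The documents do sometimes use the word loosely for that longer stretch. But SAP 4.1 uses the same day-84 expression for a period that begins at auto-mode activation, and nothing ties the count in 7.6 to pump start.

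The other objections concern size, and they stand. Early activation is optional. The 25% cap covers all 670G users, not only those in auto mode. Uniform timing is an assumption. Rejection needs a gap of at least 8 days on the main count and a visit in the last 1 to 3 days of its window. HbA1c and BMI are secondary outcomes, and the models in SAP 7.3 and 7.4 use baseline and both periods, so a rejected value need not remove the participant's other data. No bias or loss of precision has been calculated, and none should be inferred.

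**Conclusion.** The mismatch is real on the better reading of the text, and minor. Applied literally, SAP 7.6 can set aside on-schedule HbA1c and BMI values on days 99 to 101 after activation, only from 670G 3.0 periods of prior 670G auto-mode users who activate early. All other periods are unaffected, provided activation and confirmation are no more than 7 days apart.

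The likely loss is between 0 and about 7 values of each measure. The upper end needs the full cap of about 28 participants, all activating on day 0, uniform timing, and the activation day counted as day 1. The result also depends on visits being counted from site confirmation. This is a low-priority clarification. What makes it worth making is that the loss, however small, would fall on the control system alone and is easy to avoid.

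**What to change.** In SAP 7.6, centre the ±14-day window on day 84 after the site-confirmed auto-mode date that schedules the visit, and require the sample to be taken before the switch to the next period's system. The condition should be no stricter than that: requiring the participant still to be using the assigned system would exclude people who stopped it early, against the intention-to-treat rule in SAP 5.1. Separately, reconcile footnote 1 of Protocol Table 2 with Protocol 5.1.4, so that one date is stated as the anchor for visits.

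The cost is one line of SAP wording and a protocol clarification, with no new data or visits. There is a modest downside: HbA1c and BMI would run on a slightly different clock from the CGM outcomes, and a late sample from an early activator could be accepted up to 10 + 98 = 108 days after activation.

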## 322 **8. Safety Analyses**

### 323 **8.1 Definitions**

324 Reportable adverse events for this protocol include all serious adverse events (SAE), adverse  
325 device effects, adverse events occurring in association with a study procedure, severe  
326 hypoglycemia (SH), and diabetic ketoacidosis (DKA) as defined in the protocol.

## 327 **8.2 Adverse Events Summary**

328 All episodes of SH and of DKA along with any other reportable adverse events will be listed by  
329 treatment arm from the time of enrollment to the last study visit. Separate listings will be  
330 provided for pre-randomization events and for events occurring during each treatment arm.

## 331 **8.3 Comparison of Safety Outcomes between Treatment Arms**

332 Each of the following safety outcomes will be tabulated by treatment arm:

- 333 • Number of adverse events/participants with at least one event
  - 334 ▪ Number of events meeting definition of ADE
- 335 • Number of serious adverse events/participants with at least one event
  - 336 ▪ Number of SAEs meeting definition of UADE
- 337 • Listing of hospitalizations and reasons for the hospitalization
- 338 • Severe Hypoglycemic Events
  - 339 ▪ Number of severe hypoglycemic events as defined in the protocol/number of  
340 participants with an event
  - 341 ▪ Number of severe hypoglycemic events associated with seizure or loss of  
342 consciousness/number of participants with at least one event
- 343 • Diabetic Ketoacidosis
  - 344 ▪ Number of diabetic ketoacidosis events, as defined in the protocol/number of  
345 participants with an event

346 Of the outcomes listed above, only the ones involving SH or DKA events will be compared  
347 between treatment arms, if there are at least five events across the two treatment arms. The others  
348 will only be tabulated by treatment arm.

349 All of the above safety outcomes will be tabulated for all subjects (including dropouts and  
350 withdrawals) for their entire period of study participation. Any adverse events that occurred prior  
351 to the start of period 1 (as defined above) will not be included in the treatment arm comparisons  
352 listed above. Each period will inclusively consist of all days in between the start of the period  
353 and the 12-week visit date.

354 If there are enough SH and DKA events associated with each treatment arm to allow for formal  
355 statistical modeling, then treatment arm comparisons will be performed for the SH and DKA  
356 outcomes listed above. For binary outcomes, repeated measures logistic regression models  
357 adjusting for period, pre-study 670G system use, HbA1c at randomization, and whether the  
358 subject experienced any events in the 12 months prior to enrollment will be used to compare  
359 treatment groups. If the model does not converge, a mid-p binomial test will be considered. For  
360 counts, the treatment groups will be compared using repeated measures Poisson regression  
361 models adjusting for period, pre-study 670G system use, HbA1c at randomization, and whether  
362 the subject experienced any events in the 12 months prior to enrollment.

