**Table 2. Schedule of Visits and Procedures During the Crossover Trial**

Randomization	Auto Mode Initiation	Crossover Period 1 (P1)							Auto Mode Initiation	Crossover Period 2 (P2)							
		Time from Auto Mode Initiation								Time from Auto Mode Initiation							
-6-10d 	0d 	24  hours	5d  ± 2d	2w ± 4d	4w ± 4d	6w ± 4d	9w ± 4d	12w + 7d (and -6-10d from P2  )	0d 	24  hours	5d  ± 2d	2w ± 4d	4w ± 4d	6w ± 4d	9w ± 4d	12w + 7d	
Visit (V) or Contact (C)	V	C	C	C	V	C	V	C	V	C	C	C	V	C	V	C	V/C
Re-review of eligibility	X																
Assessment visit	X			X		X			X			X		X		X	
Height, weight, blood pressure	X								X							X	
Central lab – HbA1c	X								X							X	
Central lab – random C-peptide and glucose	X																
Auto mode training	X																
Turn auto mode on		X								X							
Setpoint evaluation 				X	X	X	X						X	X	X	X	
Questionnaires - Diabetes Tech Attitude + Human Factors									X							X	
AE Assessment	X	X	X	X	X	X	X	X	X	X	X	X	X	X	X	X	
Upload device data from home		X	X	X		X		X		X	X	X		X		X	
Upload device data at clinic visit	X				X		X		X				X	X		X	
Review glucose patterns	X	X	X	X	X	X	X	X	X	X	X	X	X	X	X	X	
Pregnancy test 	X																

Auto mode initiation will begin 6-10 days after Randomization and after end of Period 1. All follow-up visits are relative to the day auto mode is initialized.

Setpoint evaluation will occur for 670G 4.0 AHCL users

Additional pregnancy tests to be performed any time pregnancy is suspected

Contacts must be completed by phone.

225  
226

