### 1716 10.7 Analysis of the Secondary Endpoints

1717 Secondary CGM-measured glycemic metrics will be calculated in the same way as the co-  
1718 primary outcomes.

1719

1720 Mean  $\pm$  SD or percentiles appropriate to the distribution for above secondary outcomes will be  
1721 reported by treatment period. For each secondary CGM metric, a repeated measures least squares  
1722 regression model with an unstructured covariance structure will be fit to compare the two  
1723 treatments by adjusting for period, pre-study 670G system use, and HbA1c at randomization as  
1724 fixed effects. For those metrics which have highly skewed distribution, a ranked normal score  
1725 transformation of outcome data will be applied in the regression model.

1726

1727 For comparing changes in HbA1c and BMI over each treatment period, the least squares  
1728 regression models will adjust for period, pre-study 670G system use, and HbA1c at  
1729 randomization. The model for BMI will additionally adjust for baseline value, age, and sex.

1730

1731 Monthly trends for selected secondary outcomes will be evaluated using boxplots.

1732

1733 **10.8 Safety Analyses**

1734 All reportable adverse events will be tabulated by treatment group from the time of enrollment  
1735 through the last study visit. Events will be separately listed in detail and tabulated for the pre-  
1736 randomization period and each study period. Coding will use the Medical Dictionary for  
1737 Regulatory Activities (MedDRA).

1738

1739 In addition, the following will be tabulated by treatment arm:

- 1740 • Number of adverse events/ participants with at least one event
  - 1741 ○ Number of events meeting definition of ADE
- 1742 • Number of serious adverse events/participants with at least one event
  - 1743 ○ Number of SAEs meeting definition of UADE
- 1744 • Listing of hospitalizations and reasons for the hospitalization
- 1745 • Severe Hypoglycemic Events
  - 1746 ○ Number of severe hypoglycemic events as defined in the protocol/number of  
1747 participants with an event
  - 1748 ○ Number of severe hypoglycemic events associated with seizure or loss of  
1749 consciousness/number of participants with at least one event
- 1750 • Diabetic Ketoacidosis
  - 1751 ○ Number of diabetic ketoacidosis events, as defined in the protocol/number of  
1752 participants with an event

1753

1754 If there are enough observed events to allow formal statistical modelling the following analyses  

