#### **Interpretation of Various Scenarios of Non-inferiority (NI) and Superiority for Treatment Group Comparison of Time Below 54 mg/dl**

\* NI refers to non-inferiority of PID + Fuzzy Logic compared with PID with a non-inferiority limit of  $\Delta=2\%$  time below 54 mg/dl.

246

247 **6.2.3 Boxplots of Monthly Trends**  
248 Monthly trends for each co-primary outcome will be evaluated using boxplots. For each co-  
249 primary outcome, we expect to have 12 weeks' worth of CGM data for each subject for each  
250 treatment arm. This amounts to approximately three months' worth of data.  
251 As mentioned above, each period will be defined from the time the subject initiates auto mode  
252 until either 84 days have been included or the 12-week visit occurs (whichever comes first).  
253 Therefore, the number of days included in each period may vary across subjects. In the monthly  
254 boxplots, the first and second months will respectively include all CGM readings from the first  
255 672 hours (i.e. 24 hours/day\*28 days) and the next 672 hours. All remaining CGM readings will  
256 be included in the third month.  
257 After partitioning the data into three separate months in each period, a single value for each  
258 month will be calculated for each co-primary outcome for each treatment arm by pooling all  
259 CGM readings falling within the three disjoint windows of days that correspond to each of the  
260 three months. For the hyperglycemic outcome, only readings falling between 6:00 AM and 11:59  
261 PM will be included in the calculation. These calculated values will be used to generate boxplots  
262 displayed by treatment arm and period for each of the three months over time. Only subjects with  
263 at least 72 hours of CGM data in all three months will be included in the monthly boxplots.

264 **6.2.4 Summary Statistics by Hour of the Day**  
265 Summary statistics appropriate to the distribution for each co-primary outcome will also be  
266 displayed by treatment arm for each hour of the day. For each co-primary outcome for each  
267 period, a single value for each hour of the day will be computed by pooling all CGM readings  
268 falling within the specified hour. The hourly intervals will be left-closed and right-open (defined  
269 as 00:00-<01:00, 01:00-<02:00, etc.). The start and end of each period will be defined in the  
270 same way as described above. For the hyperglycemic outcome, summary statistics will not be  

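### Read literally, SAP 8.3 starts each safety period at auto mode activation, so the first 6-10 days on the assigned pump drop out of the arm comparisons, contrary to Protocol 10.8 and SAP 8.2

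*SAP*

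**What the plan says.** SAP 8.3 sets the safety window in two consecutive sentences. Events prior "to the start of period 1 (as defined above) will not be included in the treatment arm comparisons"; the text continues "listed above. Each period will inclusively consist of all days in between the start of the period" and the 12-week visit date.

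The earlier definition is in SAP 4.1: "In these calculations, each period will start at the time that the subject turns on auto mode". SAP 6.2.3 repeats it: "As mentioned above, each period will be defined from the time the subject initiates auto mode".

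The protocol puts that moment some days after the assigned pump is first worn. Table 2, footnote 1: "Auto mode initiation will begin 6-10 days after Randomization and after end of Period 1". Sections 5.1.2 and 5.1.3: "The system will initially be used with auto mode deactivated (except for 670G auto mode users" at screening, who may switch it on at once if they are on the 670G 3.0). There is no washout, and the Period 1 week-12 visit is day 1 of Period 2 (Protocol 5.1.3).

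Three other rules leave no gap:

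- Protocol 10.8: "All reportable adverse events will be tabulated by treatment group from the time of enrollment" to the last visit, separating the pre-randomization period from each study period.
- SAP 8.2: separate listings are "provided for pre-randomization events and for events occurring during each treatment arm".
- SAP 8.3 itself, in the sentence before the exclusion, tabulates safety outcomes over the whole of each participant's time in the study.

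**The concern.** A participant who has an event on, say, day 4 after randomization is already on the assigned pump, which may be the investigational one. Under the literal SAP 8.3 rule that event is post-randomization but precedes the start of Period 1, so it is left out of the arm comparison. A similar event on day 4 after the switch falls after the Period 1 window has closed and before the Period 2 window opens.

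The trial compares the safety of two pumps, so the rule that allocates events to arms should be unambiguous. As written, two programmers could produce different by-arm results, and the SAP 8.2 listing for an arm need not reconcile with the SAP 8.3 table for the same arm. The omission can also be unequal: prior 670G auto mode users may have no gap in their 670G 3.0 period but still have one in their AHCL period.

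**Working it through.** The plan gives no figure for this point, so there is nothing to reproduce; sample size and power do not depend on it.

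**Which days fall outside the windows, read literally**

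| Interval | Pump worn | Status under SAP 8.3 |
|---|---|---|
| Randomization to auto mode (6-10 days) | Period 1 pump | Expressly excluded from the arm comparisons |
| Auto mode to Period 1 12-week visit | Period 1 pump | Period 1 |
| Switch to auto mode (6-10 days) | Period 2 pump | In neither window; follows only from the sentence on period length |
| Auto mode to Period 2 12-week visit | Period 2 pump | Period 2 |

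**Share of on-pump days.** Share = gap / (gap + days from auto mode to the visit). The gap is 6 to 10 days; the 12-week visit falls 84 to 91 days after auto mode starts (Protocol 5.1.4).

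- Smallest: 6 / (6 + 91) = 6.2%.
- Largest: 10 / (10 + 84) = 10.6%.

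**Person-days.** Take 112 randomized (Protocol 2.1) and assume all use both pumps.

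- Per arm: 112 × 6 = 672 to 112 × 10 = 1,120.
- Both arms: 1,344 to 2,240.

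**Possible inequality.** Protocol 2.1 caps 670G users at 25%, that is 28 of 112. If all 28 used auto mode at screening and switched it on at once on the 670G 3.0 (an upper bound):

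- 670G 3.0 days left out: 84 × 6 = 504 to 84 × 10 = 840.
- AHCL days left out: 672 to 1,120, unchanged.
- Total: 1,176 to 1,960.

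**Severe hypoglycemia and DKA.** The 670G pivotal trial (Protocol 1.1.4) saw none in 12,389 patient-days. The one-sided 95% upper bound on the rate is -ln(0.05) / 12,389 = 0.000242 per day. Over 1,176 to 2,240 days that is 0.28 to 0.54 events across both periods.

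**Other events, illustration only.** These numbers matter only if the period window also governs the tabulations. They assume the pivotal trial's rates for both pumps, constant over time.

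- Device-related: 28 / 12,389 = 2.26 per 1,000 days. On 1,176 days, 2.7; on 2,240 days, 5.1. Half the rate on the fewest days gives 1.3; double the rate on the most days gives 10.1.
- Serious: 4 / 12,389. On 1,176 days, 0.4; on 2,240 days, 0.7.

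**The case against.** The strongest reply is that the sponsor probably did not mean this.

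- **The definition has a limited scope.** SAP 4.1 confines its auto mode start to the co-primary calculations, and 6.2.3 concerns CGM boxplots. The same paragraph of 4.1 also uses the ordinary sense of a period, since it expects auto mode 6-10 days after the first day of Period 2. Protocol 5.1.4 likewise begins the study period before the auto mode contact. This stands as evidence of intent. But 8.3 points back to a definition, and auto mode activation is the only explicit one there.
- **Comparisons are not tabulations.** SAP 8.3 compares only severe hypoglycemia and DKA, and only tabulates the rest. A reader might infer that by-arm counts of all adverse events, ADEs and SAEs certainly lose the early days. The documents do not support that: the express exclusion names comparisons only, and the tabulations are promised over all of participation. Those counts are cut only if the sentence on period length is applied to them too.
- **Period 2 is inferred.** A reader might also infer an express exclusion in both periods. The text excludes only events before Period 1; with no washout, assigning the later days to Period 2 is natural. The Period 2 gap arises only if the auto mode start is carried into the sentence on period length.
- **The event rate is borrowed.** The pivotal trial was in closed loop 87.2% of the time and counted skin irritation among its device-related events. The days at issue here are mostly in manual mode, and this trial does not report non-severe sensor skin reactions (Protocol 8.1.2). The device-related counts therefore show scale, not a forecast.
- **The exclusion could be justified.** Before auto mode, both pumps mostly run in manual mode with predictive suspend, and Protocol 6.1.1 describes them as identical apart from the algorithm software. Omitting those days is defensible for comparing algorithms. Protocol 10.8 does not plan it, however.

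**Conclusion.** The point holds as a conflict of wording with a real consequence if 8.3 is applied as written. On that reading, events in the 6-10 days before auto mode are expressly left out of the Period 1 arm comparisons and sit in neither window in Period 2. That is 6.2% to 10.6% of each period's on-pump days, with fewer days lost on the 670G 3.0 if prior auto mode users activate at once.

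The certain effect, still on that reading, is on the severe hypoglycemia and DKA comparison. It is small: at most about half an event at the borrowed 95% bound, in an analysis run only if at least five events occur. Any effect on the adverse event, ADE and SAE counts is conditional on the window governing the tabulations.

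No direction of bias is claimed. Every reportable event stays listed under SAP 8.2, and the co-primary results do not change. The point is minor, but worth correcting because a stated rule would remove on-treatment events that the protocol says to tabulate.

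**What to change.** In SAP 8.3, define the safety periods separately from the CGM periods. Suggested text: For safety analyses, Period 1 runs from randomization until the switch to the Period 2 pump, and Period 2 from that switch to the last study visit or contact. Events count in the arm assigned for that period, whether or not auto mode is on.

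Apply this to both the tabulations and the severe hypoglycemia and DKA comparisons. If the sponsor wants an algorithm-specific view, add counts from auto mode start as a supportive table.

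The cost is two sentences and, optionally, one table. No new data are needed: adverse events are already assessed at randomization, at auto mode initiation and at every later contact (Protocol Table 2).
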